- TREATMENT** **7-day run-in/washout periods:** Participants will be asked to consume the run-in or washout (control) diet for 7 days. A run-in period is to minimize the effect of habitual diet intake before start of intervention, a washout period is to ensure that potential cardiometabolic effect of the previous intervention diet is eliminated.
- 14-day dietary intervention periods:** Participants will consume the control or intervention diet, weekly delivered at their home. Participants will be asked to visit the Cambridge Epidemiology & Clinical Trials Unit testing sites 7 times in total (every 1st and 15th day of each intervention sequence) in fasted condition.
- Day 1 and day 15 of 14-day dietary intervention periods:** Participants will be asked to arrive in fasted condition and stay at the testing site until the last measurement has been completed. Participants will bring 24-hr urine and stool collections. The following measurements will be done: anthropometrics, bioelectrical impedance, blood pressure,

pulse wave velocity, and cognitive function. Samples of fasting blood will be taken. Participants will complete questionnaires to assess maintenance of lifestyle factors e.g. physical activity and appetite profiles throughout the study. Breakfast will be provided.

DURATION Participants will be involved for 9 weeks in total:

Week 1: Run-in period

Week 2-3: 14-day dietary intervention

Week 4: Wash-out period

Week 5-6: 14-day dietary intervention

Week 7: Wash-out period

Week 8-9: 14-day dietary intervention

OUTCOME MEASURES

Primary outcome: Changes in systolic and diastolic blood pressure (mmHg)

Secondary outcomes: Changes in:

- Arterial stiffness assessed by pulse wave velocity and pulse wave analysis
- Cardiovascular risk factors measured in fasted blood samples
- Markers of endothelial function measured in fasted blood samples
- Markers of low-grade inflammation measured in fasted blood samples
- Urinary and circulatory metabolite profiles and individual metabolite levels
- Established objective urinary and circulatory markers of intakes of fruits, vegetables, and other foods
- Composition of gut microbiota
- Cognitive function
- Average total, daytime, night time 24-hr ambulatory blood pressure (in subsample)
- Average objective physical activity intensity and sleep time (in subsample)

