4.3. Withdrawal criteria

The safety of the study participants takes priority. Any significant adverse event (as assessed by the researchers) will halt the study and the ethics committee and sponsor will be informed as per standard protocol. All adverse events will be recorded and investigators will review each adverse event as it arises. In addition, participants will be free to withdraw at any time and are not required to give a reason.

Table 4. Inclusion and exclusion criteria

Inclusion criteria:	
Age	40 to 65 years
Automated office systolic BP	Average systolic BP of 125-160 mmHg at 2 measurements separated by >30 min
Antihypertensive medication use	No use less than 3 weeks before screening
Apparently healthy condition	No reported current or previous diabetes mellitus, (secondary) hypertension, or metabolic, cardiovascular, renal, liver, thyroid, gastrointestinal diseases
Body Mass Index	20 to 35 kg/m ²
Smoking status	Non-smoker (not smoked within last 6 months)
Low habitual fruits and vegetable intake	Average fruits and vegetables intake of <4 portions per day (UK average, 40-65 yr) or willing to reduce habitual daily fruit and vegetable intake ≤2 weeks before enrollment
Exclusion criteria:	
Use of other medications	Any medications likely to interfere with energy metabolism, appetite regulation and hormonal balance, including inflammatory drugs or steroids, antibiotics, androgens, phenytoin, erythromycin or thyroid hormones and use of antibiotics.
Alcohol intake	> 21 units per week (females) or >28 units per week (male) and not willing to limit alcohol intake to maximum 1 unit/day ≤2 weeks before and during enrollment
Physical activity	≥10 h/week of moderate to vigorous physical activity
Recent weight loss or gain	≥3 kg in the preceding 3 months
Use of dietary supplements	Unwillingness to stop supplement use ≥2 weeks before enrollment and during intervention
Other medical factors	Pregnancy or lactation
Intervention specific factors	Unable or unwilling to consume provided diets during the intervention Unsufficient storage space for provided diets Food sensitivities or vegetarian/vegan diet by choice Participation in another intervention study at the same time Living >15 miles from the Cambridge Epidemiology & Clinical Trials Unit testing sites, or not willing to travel more than 15 miles No signed informed consent

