5.2. Reporting procedures

All adverse events should be reported. Depending on the nature of the event the reporting procedures below should be followed. Any questions concerning adverse event reporting should be directed to the Chief Investigator in the first instance.

Non-serious AEs

All such events, whether expected or not, should be recorded.

Serious AEs (SEAs)

An SAE form should be completed and faxed to the Chief Investigator within 24 h. However, relapse, death and hospitalisations for elective treatment of a pre-existing condition do not need reporting as SAEs.

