6. STATISTICS AND DATA ANALYSIS

The statistical power calculation is based on BP-lowering effects ($-7.6 \pm 1.4 / -5.3 \pm 1.4$ mmHg) of a DASH fruit and vegetable diet (+4.5 servings/day) vs average US diet in 15 obese hypertensive participants with an average BP of 136/90 mmHg in a 3-wk cross-over study with nutritional advice (no controlled diet).³³ Assuming a conservative detectable effect size (-1 mmHg SBP) considering differences in design and type of participants, 18 participants would be sufficient to detect a difference of 1 mmHg in SBP between groups (two-sided test at 5%, SD SBP change of 1.4 mmHg, 80% power). As we use block randomisation with 6 intervention sequences, internal independent statisticians have advised to randomise a substantial number of participants per sequences. To further strengthen the study design, we will recruit and randomise (stratified by gender) 36 participants in total – with 6 participants in each group.

Treatment effects will be calculated as the changes between values at start and end of each intervention sequence. Treatment effects will be tested by comparing changes of each of the increased fruit and vegetable interventions with changes during low fruit and vegetable period (control group), and of the citrus fruit and cruciferous vegetables period with increased commonly consumed fruit and vegetable intervention. Linear mixed models will be used for repeated measures to compare changes. Treatment and period will be set as fixed effects and subject as random effect. To test for carryover effect, the previous treatment will be included in the model. Statistical significance will be set at 2-sided P-value of 0.05. The researcher performing the statistical analyses will be blinded to the treatment groups.

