4.4 Withdrawal/loss to follow-up

The number and percentage of participants who withdraw during the study for any reason will be presented by randomised sequence.

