5.3 Safety data

The number and percentage of adverse events (AEs) will be reported by randomised sequence, overall and subdivided into non-serious AEs and serious AEs.

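### SAP 5.3 takes the adverse event as its unit, gives no denominator, and plans no count of participants with an event, so its percentage is not the proportion affected

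*SAP*

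**What the plan says.** SAP 5.3 is a single sentence: "The number and percentage of adverse events (AEs) will be reported by randomised sequence, overall and subdivided into non-serious AEs and serious AEs". It does not say what the percentage is a percentage of, or how several events in one person are handled.

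SAP 4.4, on withdrawals, names people as the unit: "The number and percentage of participants who withdraw during the study for any reason will be presented by randomised sequence".

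The protocol sets no limit on events per person. Section 4.3 says "All adverse events will be recorded and investigators will review each adverse event as it arises", and section 5.2 says of non-serious events "All such events, whether expected or not, should be recorded". On follow-up, the study summary says "Participants will be involved for 9 weeks in total", which covers run-in, three diet periods and two wash-outs.

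On cell size, Protocol section 6 refers to six intervention sequences and plans "36 participants in total – with 6 participants in each group".

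Neither document contains another rule for tabulating adverse events.

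**The concern.** A reader of a safety table normally wants to know how many of the people studied had an event, and how many had a serious one. SAP 5.3 does not ask for that number. Every event is recorded over nine weeks, and each participant passes through three diets, so one person may report the same complaint more than once. With about six people per column, one such person can fill most of a cell. A percentage beside the count then invites the reader to take it as the proportion of people affected, which it is not under any literal reading. No other safety summary is planned that would correct the impression.

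**Working it through.** **Inputs from the documents.** 36 participants over 6 sequences (Protocol section 6), so 36 / 6 = 6 per sequence, matching the protocol's own figure. This is the planned size. Actual sizes are not given, and SAP 5.2.1 mentions six individuals whose sequences were mixed up. SAP 5.3 contains no figure to reproduce.

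**Literal readings of the percentage.** Let E be the events in a sequence, T all events in the trial, and n = 6 the participants in the sequence.

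- Share of events, E / T. It sums to 100% across sequences however many people were affected, and cannot exceed 100%. A share taken within a sequence (serious or non-serious events over E) describes the mix of events only.
- Events per participant, E / n. Repeat events count as if they were new people, and there is no upper limit: 7 events among 6 people give 7/6 = 116.7%.

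The quantity usually wanted is A / n, where A is the number of participants with at least one event. It lies between 0% and 100%.

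**Example without any assumed rate.** Sequence A: one person has 6 events and five have none. Sequence B: six people have 1 event each.

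- E / T is 6/T for both, whatever T is.
- E / n is 6/6 = 100% for both.
- A / n is 1/6 = 16.7% for A and 6/6 = 100% for B.

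A less extreme case: event counts of 4, 2, 1, 0, 0, 0 give E / n = 7/6 = 116.7% and A / n = 3/6 = 50.0%.

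**Illustration with assumed rates.** The documents give no event rate, so the mean m per person over nine weeks is assumed to lie between 0.25 and 2. With Poisson counts the proportion affected is 1 − e^(−m). With counts clustered in some people (gamma-Poisson, shape k) it is 1 − [k/(k+m)]^k. The last column is the Poisson chance that six people have more than 6 events in total.

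| m | E / n expected | Affected, Poisson | Affected, k = 1 | Affected, k = 0.5 | Chance that E / n exceeds 100% |
|---|---|---|---|---|---|
| 0.25 | 25% | 22.1% | 20.0% | 18.4% | 0.1% |
| 0.5 | 50% | 39.3% | 33.3% | 29.3% | 3.4% |
| 1 | 100% | 63.2% | 50.0% | 42.3% | 39.4% |
| 2 | 200% | 86.5% | 66.7% | 55.3% | 95.4% |

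Across this range, events per participant exceed the proportion affected by a factor of 1.1 (0.25/0.221) to 3.6 (2/0.553). The factor is close to 1 when events are rare and grows with the rate and the clustering.

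**The case against.** The best reply is that the sentence is loose shorthand, that it never calls its percentage a risk, and that a share of events split by seriousness is a coherent description. The wording of SAP 4.4 proves little about intent, since a person withdraws only once and participants is the natural word there. This is fair as to what the authors may have meant. It does not change what the text asks for. If participants with an event were intended, the rewording simply says so.

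Three stronger inferences are tempting, and the documents do not support them.

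- That the planned percentage will exceed 100%. This needs participants as the denominator, and SAP 5.3 names none. As a share of events it is capped at 100%.
- That the trial will be unable to say how many participants had an event. All events are to be recorded, so the number can be derived. The plan just does not call for it.
- That the table above measures the distortion in this trial. Its rates and clustering are assumptions. At 0.25 events per person the effect is small.

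It is also true that this is a pilot study of ordinary foods, that adverse events are not a listed outcome, and that no safety test is planned. That bears on the weight of the point, not on whether it is correct.

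**Conclusion.** The point holds in a limited form. SAP 5.3 counts events, leaves the denominator undefined, and plans no participant-level summary. Its percentage, followed literally, is not the proportion of participants affected and cannot tell repeat events in one person from events in several people. The two-sequence example shows this with only the planned size of six: identical entries for 17% and 100% of participants affected. How far the reported figure would mislead in practice depends on an event rate and clustering that the documents do not give.

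The severity is minor: neither the blood pressure analysis nor any secondary outcome analysis is touched.

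A separate matter is that every sequence contains all three diets, so a table by sequence cannot attribute events to a diet. Changing the unit does not solve that, and changing the columns would not solve the unit.

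**What to change.** Reword SAP 5.3 along these lines: for each column of the adverse event table (randomised sequence as now planned, and any further grouping), report how many participants, and what percentage, had at least one AE, at least one non-serious AE and at least one serious AE. The denominator is all participants randomised to that sequence, or all those exposed in that grouping. The total number of events is given alongside as a count without a percentage.

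The denominator should be written out and not left to the analysis population of SAP 3.3. That population requires an outcome at the end of at least one period, so it would omit anyone who had an event and left before then.

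The cost is a short rewording and one de-duplication by participant identifier. No new data are needed. The drawback is that a participant percentage hides repeat events, which is why the event count stays beside it.
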